8.3.8 Adverse Events of Special Interest

Adverse events of special interest are required to be reported by the investigator to the Sponsor immediately (i.e., no more than 24 hours after the investigator becomes aware

of the event; see Section A3–5 for reporting instructions). Adverse events of special interest for this study are as follows:

- Cases of potential drug-induced liver injury that include an elevated ALT or AST ($>3 \times \text{ULN}$) in combination with *either an elevated total bilirubin ($>2 \times \text{ULN}$) or clinical jaundice, as defined by Hy's Law (see Section A3–7.6)*
- *Cases of an elevated ALT and/or AST $3\text{--}5 \times \text{ULN}$, $\text{INR} > 1.5$, total bilirubin $\leq 2 \times \text{ULN}$, and absence of clinical jaundice*
- *Cases of elevated ALT and/or AST $5\text{--}8 \times \text{ULN}$, total bilirubin $\leq 2 \times \text{ULN}$ and absence of clinical jaundice*
- *Cases of elevated ALT and/or AST $> 8 \times \text{ULN}$, total bilirubin $\leq 2 \times \text{ULN}$ and absence of clinical jaundice*
- Suspected transmission of an infectious agent by a study treatment, as defined below:

Any organism, virus, or infectious particle (e.g., prion protein transmitting transmissible spongiform encephalopathy), pathogenic or non-pathogenic, is considered an infectious agent. A transmission of an infectious agent may be suspected from clinical symptoms or laboratory findings that indicate an infection in a participant exposed to a medicinal product. This term applies only when a contamination of the study treatment is suspected.

Laboratory results for adverse events of special interest pertaining to hepatic transaminase elevations should be closely monitored, as the AESI category should be upgraded to reflect the most severe liver enzyme results, where required.

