A3-7.1 DIAGNOSIS VERSUS SIGNS AND SYMPTOMS

A diagnosis (if known) should be recorded on the Adverse Event eCRF rather than individual signs and symptoms (e.g., record only liver failure or hepatitis rather than jaundice, asterixis, and elevated transaminases). However, if a constellation of signs and/or symptoms cannot be medically characterized as a single diagnosis or syndrome at the time of reporting, each individual event should be recorded on the Adverse Event eCRF. If a diagnosis is subsequently established, all previously reported adverse events based on signs and symptoms should be nullified and replaced by one adverse event report based on the single diagnosis, with a starting date that corresponds to the starting date of the first symptom of the eventual diagnosis.

A3–7.2 ADVERSE EVENTS THAT ARE SECONDARY TO OTHER EVENTS

In general, adverse events that are secondary to other events (e.g., cascade events or clinical sequelae) should be identified by their primary cause, with the exception of severe or serious secondary events. A medically significant secondary adverse event that is separated in time from the initiating event should be recorded as an independent event on the Adverse Event eCRF. For example:

- If vomiting results in mild dehydration with no additional treatment in a healthy adult, only vomiting should be reported on the eCRF
- If vomiting results in severe dehydration, both events should be reported separately on the eCRF
- If a severe gastrointestinal hemorrhage leads to renal failure, both events should be reported separately on the eCRF
- If dizziness leads to a fall and consequent fracture, all three events should be reported separately on the eCRF
- If neutropenia is accompanied by an infection, both events should be reported separately on the eCRF

All adverse events should be recorded separately on the Adverse Event eCRF if it is unclear as to whether the events are associated.

A3–7.3 PERSISTENT OR RECURRENT ADVERSE EVENTS

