Appendix 6: Safety Plan: Management of Identified and Potential Risks

Table A6-1 Guidelines for Management of Participants Who Experience Adverse Events (cont.)

AST or ALT > 3 × ULN in combination with a total bilirubin > 2 × ULN or INR > 1.5, or clinical jaundice
	
 • Permanently discontinue study drug. • Rapid evaluation, including repeat testing of ALT, AST, ALP, total and direct bilirubin, GGT, CPK, LDH, complete blood count with differential, coagulation tests, and the “LFT unscheduled” lab kit within 48-72 hours; inquire about symptoms, co-medications, co-morbidities, and work-up for alternative etiologies, and hepatology or subspecialist consultation is required (refer to Appendix 7). The medical monitor will provide guidance on additional lab testing that may be required. • Continue close observation (repeat testing of ALT, AST, ALP, and total bilirubin) every 48-72 hours until transaminases stabilize, then weekly until AST and ALT < 3 × ULN. • Report as an adverse event of special interest within 24 hours, (see Section 8.3.8).

ALT and/or AST 3-5 × ULN, INR > 1.5, total bilirubin ≤ 2 × ULN, and absence of clinical jaundice
	
 • Permanently discontinue study drug. • Rapid evaluation, including repeat testing of ALT, AST, ALP, total and direct bilirubin, GGT, CPK, LDH, complete blood count with differential, coagulation tests, and the “LFT unscheduled” lab kit within 48-72 hours; inquire about symptoms, co-medications, co-morbidities, and work-up for alternative etiologies, and hepatology or subspecialist consultation is required (refer to Appendix 7). The medical monitor will provide guidance on additional lab testing that may be required. • Continue close observation (repeat testing of ALT, AST, ALP, and total bilirubin) every 48-72 hours until transaminases stabilize, then weekly until AST and ALT < 3 × ULN. • Report as an adverse event of special interest within 24 hours, (see Section 8.3.8).

LFT=liver function test; LLN=lower limit of normal; PLT = platelet count; ULN=upper limit of normal

- ^a Appropriate laboratory investigations, including but not limited to cultures, should be performed to establish the etiology of any serious infection.

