Management of participants with sustained QTcF prolongation should include close monitoring, with ECGs repeated at least hourly until two successive ECGs show resolution of the findings, correction of any electrolyte abnormalities, and possible discontinuation of other concomitant medications that are known to prolong the QT interval. Consultation with a cardiologist or electrophysiologist is recommended, to help in the management of such participants.

Appendix 7

Guidance for Recording Information in eCRFs for Participants with Abnormal Liver Enzyme and Function Tests

For any patient with ALT/AST > 3 ´ ULN, please ask the questions below and record the relevant information in the appropriate eCRF.

Liver Related Signs and Symptoms

1). Does the subject have any of the following liver-related signs and symptoms?:

- a) Fever
- b) Nausea
- c) Vomiting
- d) Abdominal pain
- e) Abdominal tenderness
- f) Joint pain/ arthralgia
- g) Joint swelling
- h) Rash
- i) Urticaria
- j) Mucosal inflammation or ulceration
- k) Asterixis
- l) Confusion/ disorientation
- m) Coma
- n) Jaundice
- o) Ascites
- p) Peripheral oedema
- q) Palmar erythema
- r) Fatigue
- s) Lymphadenopathy
- t) Dark urine
- u) Other liver-related signs or symptoms

If “Yes” to Question 1.; if ALT/AST >5 x ULN, please report each symptom on the DILI Signs and Symptoms eCRF.

If ALT/AST > 3 and ≤5 ´ ULN, please report each sign and symptom in the additional case details of the Abnormal Liver Enzyme Adverse Event eCRF (unless a specific diagnosis has been established that accounts for the symptom, in which case the specific diagnosis should be recorded).

Appendix 7: Guidance for Recording Information in eCRFs for Patients with Abnormal Liver Enzyme and Function Tests cont.

Medical history: Liver-Related Diseases

2. Does the subject have a history of any of the following?

- a) Hepatitis A
- b) Hepatitis B
- c) Hepatitis C
- d) Hepatitis D
- e) Hepatitis E
- f) Autoimmune hepatitis
- g) Haemochromatosis
- h) Non-alcoholic fatty liver disease (NAFLD)
- i) Non-alcoholic steatohepatitis (NASH)
- j) Gallbladder disease
(e.g., gallbladder stones, cholecystitis, bile duct stones)
- k) Alcohol-related liver disease
(e.g., alcohol related cirrhosis, alcohol related hepatitis, steatosis)
- l) Drug-induced liver injury (DILI)
(Specify suspected drugs)
- m) Jaundice or hyperbilirubinaemia
- n) HIV infection
- o) Tuberculosis
- p) Congestive heart failure
- q) Right heart failure
- r) Hepatic metastasis

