- s) Diabetes
- t) Inflammatory bowel disease
(Crohn's disease or ulcerative colitis)
- u) Hypotension

If "Yes" to question 2:

please report each liver-related disease on the Medical History/Baseline conditions eCRF as per protocol Section [8.2.1](#)

Appendix 7: Guidance for Recording Information in eCRFs for Patients with Abnormal Liver Enzyme and Function Tests cont.

v) Systemic infection or sepsis

w) Seizures

x) Recent drop in blood pressure or shock

y) Herpes infection

z) Uncontrolled diabetes mellitus

Appendix 7: Guidance for Recording Information in eCRFs for Patients with Abnormal Liver Enzyme and Function Tests cont.

Risk Factors for Conditions Associated with Liver Disease	
Has any of the following occurred within 1 week before the hepatic event?	
3. Did the subject engage in vigorous physical exercise?	If "Yes" for Question 3, please record in the "Additional Case Details" field of the hepatic adverse event that was reported.
4. Has the subject taken acetaminophen (paracetamol)?	If "Yes" for Questions 4-6: please report on the Concomitant Medications eCRF (as per protocol Section 6.8).
5. Have any other new medications or supplements been taken?	
6. Did the subject eat wild mushrooms?	
Has any of the following occurred within 3 months before the hepatic event?	
7. Has the subject gained or lost weight considered to be clinically significant?	If "Yes" for Question 7: please report on an Adverse Event eCRF (unless a diagnosis of liver injury has been established).
8. Has the subject consumed alcohol?	If "Yes" for Question 8: please complete the Alcohol Use History eCRF.
 
The chart displays the following alcohol units for various beverages:
 
 1 UNIT: Single shot of spirits (25ml, ABV 40%) 1.5 UNITS: Alcopop (275ml, ABV 5.5%) 1.5 UNITS: Small glass of red / white / rosé / sparkling wine (125ml, ABV 12%) 2 UNITS: Can of beer, ale, lager or cider (440ml, ABV 5.5%) 2.1 UNITS: Standard glass of red / white / rosé / wine (175ml, ABV 12%) 3 UNITS: Pint of beer, ale, lager or cider (568ml, ABV 5.2%) 3 UNITS: Large glass of red / white / rosé / wine (250ml, ABV 12%) 9 UNITS: Bottle of red / white / rosé / sparkling wine (750ml, ABV 12%) 	
9. Has the subject been exposed to an environmental or industrial toxin or a chemical agent?	If "Yes" for Question 9, please record in the "Additional Case Details" field of the hepatic adverse event that was reported.

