#### **5.4.2.1 Secondary safety endpoints**

Safety will be assessed through summaries of exposure to study treatment, adverse events, changes in laboratory test results, changes in vital signs, and by the proportion of patients with suicidal ideation or behavior as assessed by Columbia-Suicide Severity Rating Scale (C-SSRS) scores.

All verbatim adverse event terms will be mapped to Medical Dictionary for Regulatory Activities (MedDRA) thesaurus terms, and adverse event severity will be graded according to the most current version of National Cancer Institute Common Terminology Criteria for Adverse Events (NCI CTCAE). All adverse events, serious adverse events, adverse events leading to death, adverse events of special interest, and adverse events leading to study treatment discontinuation that occur on or after the first dose of study treatment (i.e., treatment-emergent adverse events) will be summarized by mapped term, appropriate thesaurus level, and severity grade. For events of varying severity, the highest grade will be used in the summaries. Deaths and cause of death will be summarized.

Relevant laboratory and vital signs will be displayed by time and grade identified when associated with an adverse event. Additionally, a shift table of selected laboratory tests will be used to summarize the baseline and maximum postbaseline severity grade. Changes in vital signs will be summarized.

Proportion of participants with suicidal ideation or behavior, as assessed by Columbia-Suicide Severity Rating Scale, will be summarized.

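### Appendix 7 sends undiagnosed symptoms at ALT/AST > 3 to 5 × ULN to a narrative field, at odds with A3-7.1 and with the events of special interest that start at 3 × ULN

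*Protocol*

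**What the plan says.** Protocol Appendix 7 applies to any participant with ALT/AST above 3 × ULN. Its first question lists liver-related signs and symptoms, among them jaundice, confusion, coma, rash and fatigue. A positive answer is then routed by enzyme level alone:

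- Above 5 × ULN: "if ALT/AST >5 x ULN, please report each symptom on the DILI Signs and Symptoms eCRF".
- Above 3 and up to 5 × ULN: "please report each sign and symptom in the additional case details of the Abnormal Liver Enzyme Adverse Event eCRF", unless a specific diagnosis accounts for the symptom and is recorded instead.

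Other parts of the protocol draw the line at 3 × ULN:

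- Section 8.3.8 lists as an adverse event of special interest (AESI) "Cases of potential drug-induced liver injury that include an elevated ALT or AST" above 3 × ULN together with bilirubin above 2 × ULN or clinical jaundice. It adds a category for 3–5 × ULN with INR above 1.5.
- Table A6-1 gives the latter its own row ("ALT and/or AST 3-5 × ULN, INR > 1.5, total bilirubin ≤ 2 × ULN, and absence of clinical jaundice"). It has a further row for enzymes above 3 × ULN with symptoms such as fatigue, nausea, fever or rash, to be recorded as an adverse event or AESI.
- Appendix 3, A3-7.1, says that when signs or symptoms cannot be brought under one diagnosis, "each individual event should be recorded on the Adverse Event eCRF".

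On analysis, SAP 5.4.2.1 works from event terms: "All verbatim adverse event terms will be mapped to Medical Dictionary for Regulatory Activities (MedDRA) thesaurus terms". It summarises adverse events, AESIs and events leading to discontinuation, and adds a laboratory shift table. It does not mention the DILI Signs and Symptoms eCRF or the case-details text.

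**The concern.** Between 3 and 5 × ULN the symptom helps decide what kind of event the participant has. In Table A6-1 an isolated rise in this band is recorded as an adverse event. The same rise with jaundice is a potential Hy's Law AESI, and with fatigue, nausea or rash it falls under a different row with a different consequence for study drug. This is the band in which Appendix 7 moves the symptom from a structured form to text.

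A site holding both A3-7.1 and Appendix 7 cannot tell whether the case-details entry replaces the separate adverse event term or supplements it. Two sites could code the same presentation differently. Transaminase elevation is a recognised risk of fenebrutinib, and Appendix 6 (A6-1.3) says it is unknown whether more severe liver injury can occur. The symptom profile of each of these few cases therefore matters for the safety assessment.

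**Working it through.** The plan states no figure on this point, so there is none to reproduce. The check has two parts: the passages side by side, and the likely number of participants.

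**1. The same case under each rule (no unifying diagnosis)**

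| Presentation | Section 8.3.8 / Table A6-1 | Appendix 7 records the symptom in | A3-7.1 records the symptom as |
|---|---|---|---|
| > 3 to 5 × ULN with fatigue, nausea, fever or rash | adverse event or AESI | case details | its own adverse event |
| > 3 to 5 × ULN with jaundice | AESI (potential Hy's Law) | case details | its own adverse event |
| > 3 to 5 × ULN, INR > 1.5, any symptom | AESI | case details | its own adverse event |
| > 5 × ULN with a symptom | AESI | DILI Signs and Symptoms eCRF | its own adverse event |

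Two of the four hepatic AESI categories can arise at 3–5 × ULN, and neither opens the DILI form there.

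The documents support reading case details as narrative. A later row of Appendix 7 names the field as case details and event narrative together. A3-7.11 has sites write a description of a medication error there. A3-7 allows one term per event field, so a symptom placed in the details of the enzyme event is not itself an event term.

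**2. How many participants**

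Inputs: 68 on fenebrutinib and 34 on placebo (Protocol 9.2, SAP 3). Earlier rates of elevation at 3–5 × ULN or higher are 1% to 10% on fenebrutinib 200 mg BID and below 1% on placebo (Appendix 6, A6-1.1). The 5% fenebrutinib rate and the 0.5% placebo rate below are illustrative values inside those ranges.

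Expected count = arm size × rate:

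- Fenebrutinib: 68 × 0.01 = 0.68, to 68 × 0.10 = 6.8.
- Placebo: below 34 × 0.01 = 0.34.

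Share of cases in the fenebrutinib arm = 68·pF / (68·pF + 34·pP):

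| Placebo rate | pF = 1% | pF = 5% | pF = 10% |
|---|---|---|---|
| 1% (ceiling) | 0.68/1.02 = 67% | 3.4/3.74 = 91% | 6.8/7.14 = 95% |
| 0.5% | 0.68/0.85 = 80% | 3.4/3.57 = 95% | 6.8/6.97 = 98% |

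Chance of at least one case = 1 − (1 − p)^n: fenebrutinib 1 − 0.99^68 = 49.5% to 1 − 0.90^68 = 99.9%; placebo at most 1 − 0.99^34 = 28.9%.

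These counts cover every elevation from 3 × ULN upward, including those above 5 × ULN that do get the form. Participants in the 3–5 × ULN band with an undiagnosed symptom are a subset. No rate is given for that subset, nor for Hy's Law or INR-defined cases within it.

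**The case against.** The strongest reply is that tiered symptom capture is a legitimate design choice and loses no hepatic event. That largely stands. A3-7.4 requires every ALT/AST above 3 × ULN to be reported as an adverse event, and A3-7.6 sends the Hy's Law and INR-defined cases to the Adverse Event eCRF within 24 hours as serious events or AESIs. The SAP tabulates these, along with discontinuations and laboratory shifts.

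It can also be said that A3-7.1 itself prefers a diagnosis to its component symptoms, that A3-7.6 allows the abnormal laboratory value to be recorded when no diagnosis is reached, and that Appendix 7 never says its entry replaces an adverse event term. This narrows the conflict to cases without a diagnosis. It does not remove it, because there A3-7.1 asks for separate events and Appendix 7 asks for text inside one event.

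A further fair point is that the SAP does not tabulate the DILI form either. Opening that form lower down would not by itself change any planned adverse event table. Finally, the eCRF specification is not among the documents, so whether the case-details text is reviewed or coded later cannot be established.

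**Conclusion.** The inconsistency is real, and its effect is limited to how symptoms are coded and described. At > 3 to 5 × ULN without a diagnosis, symptom terms may be entered by some sites and left in narrative by others, including in cases the protocol classes as AESIs. Each affected participant already carries a mandatory enzyme event or a diagnosis, so the proportion with any adverse event does not change; counts of individual symptom terms may. The primary analysis is untouched. If the earlier rates apply here, fewer than about 7 participants would be expected on fenebrutinib, and fewer than one on placebo, with any elevation from 3 × ULN upward. The number actually affected is smaller and cannot be derived.

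A reader might infer three stronger conclusions, which the documents do not support:

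- *That Hy's Law or INR-defined events at 3–5 × ULN vanish from the structured safety data.* They remain as adverse events, AESIs, discontinuations and laboratory values.
- *That the arm comparison is biased in the drug's favour by a definite amount.* More cases are expected on fenebrutinib, but the share runs from 67% to 95% with placebo at its ceiling. The rates include elevations above 5 × ULN, and no document says how often a symptom would go otherwise unrecorded.
- *That Question 2 of Appendix 7 diverts new on-treatment events, such as "x) Recent drop in blood pressure or shock", into baseline history.* The question asks about a history of conditions, its table is broken across pages in the text available, and Section 8.3.1 and A3-1 still make new on-treatment conditions adverse events.

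**What to change.** Reconcile Appendix 7 with Section 8.3.8, A3-7.1 and Table A6-1 on recording only:

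1. State in Appendix 7 that signs and symptoms at ALT/AST above 3 × ULN without a unifying diagnosis are also entered as adverse event terms under A3-7.1. This is the step that makes symptom coding consistent in the SAP tables.
2. Require the DILI Signs and Symptoms eCRF for every hepatic AESI in Section 8.3.8, whatever the enzyme level. This gives the Hy's Law and INR-defined cases at 3–5 × ULN the same structured symptom data as cases above 5 × ULN.

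The cost is an edit to the appendix and to the eCRF completion guidance, and a few more forms and event entries. No dosing or stopping rule, endpoint or planned analysis changes.

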Appendix 8 Guidance for Diagnosis of Progressive Multifocal Leukoencephalopathy

ACTION STEPS IF PROGRESSIVE MULTIFOCAL LEUKOENCEPHALOPATHY IS SUSPECTED

Participants with suspected progressive multifocal leukoencephalopathy (PML), defined as a new or worsening neurological symptom that necessitates magnetic resonance imaging (MRI) and/or lumbar puncture and cerebrospinal fluid (CSF) analyses to rule out PML, should be withheld from study treatment until PML is ruled out by complete serial clinical evaluations and appropriate diagnostic testing. The Medical Monitor should be contacted by email and should be immediately contacted by telephone.

If the clinical presentation is suggestive of PML, further investigations should include brain MRI evaluation as soon as possible. If MRI evaluation reveals lesions suspicious for PML (see [Figure A8-1](#)), a lumbar puncture with evaluation of the CSF for the detection of JC virus (JCV) DNA using a validated sensitive assay should be undertaken. A diagnosis of PML can potentially be made by evaluating clinical and MRI findings plus the identification of JCV in the CSF (see [Table A8-1](#)).

There is no known treatment or cure for PML. Treatment considerations are discussed in the medical literature (Calabrese et al. 2007)

MRI ASSESSMENT

Although there are no pathognomonic findings that differentiate PML from multiple sclerosis (MS), a brain MRI scan that includes fluid-attenuated inversion recovery (FLAIR) and T2-weighted and T1-weighted sequences, with and without gadolinium (Gd), should be performed to assess participants with neurological changes suggestive of PML (see [Figure A8-1](#)).

Comparison with a baseline scan may assist with interpretation of the findings on the newly acquired MRI scan (see [Table A8-2](#)) for differences in lesion characteristics that may help differentiate between PML and MS).

CSF ASSESSMENT

[figure not shown]
The detection of JCV DNA in the CSF of a patient with clinical and MRI features suggestive of PML establishes the diagnosis of PML.

If JCV DNA is not detected in CSF and if clinical suspicion of PML remains high, a repeat lumbar puncture should be performed.

If diagnosis remains uncertain and suspicion of PML remains high, a brain biopsy may be considered to establish a definitive diagnosis.

Appendix 8: Guidance for Diagnosis of Progressive Multifocal Leukoencephalopathy

Figure A8-1 Diagnostic Algorithm Framework for PML

CSF = cerebrospinal fluid; FLAIR = fluid-attenuated inversion recovery; JCV = JC virus; MRI = magnetic resonance imaging; MS = multiple sclerosis; PML = progressive multifocal leukoencephalopathy; PRES = posterior reversible encephalopathy syndrome; PCR = polymerase chain reaction; VZV = varicella zoster virus.

Source: Berger et al. 2013

